## **Statistical analysis**

Statistical analysis to be used will be performed using Student's *t*-Test, after confirming the normal distribution of the sample, otherwise, a mathematical transformation of the data will be performed to obtain a Gaussian curve. If there is no statistical difference between the groups, cervical dilation between each group can be verified with the Pearson (or Spearman) test using the continuous variables of both groups (dilation), or the chi-square test dilation <8, ≥8mm. If there is a statistical difference between the groups, the correlations will be by groups, i.e., 400 µg and 200 µg.

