## **STUDY GOALS**

### **Primary**

To verify if a dose of 200 µg of misoprostol results in a cervical priming is not

less than 25% at the dose of 400 µg usually used.

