## **Secondary**

To verify if there is a relationship between the dose of misoprostol and the degree of cervical dilation ( $\geq 8\text{mm}$  /  $<8\text{mm}$ ).

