## **HYPOTHESIS**

Our null hypothesis is that  $P_{\text{standard (400µg)}} \geq P_{\text{alternative (200µg)}} + 25\%$ ;

Our alternative hypothesis is that  $P_{\text{standard (400µg)}} - 25\% < P_{\text{alternative (200µg)}}$ .

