## **Variables:**

1. The control group (400 µg misoprostol);
2. The experimental group (200 µg misoprostol);
3. Cervical dilation present or not.

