## **Outcomes**

The following outcomes will be determined:

1. Dilatation of the cervix without the need for a dilator between 3 and 6 hours after placing the misoprostol;
2. Dilatation of the cervix with 8mm. The measurement of cervical dilation will be done with a Karmann cannula, starting with the largest diameter (11 mm) and decreasing until it was possible to introduce, without resistance, the cannula into the uterine cavity (continuous variable 4 to 11).

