## **Sample size**

The sample size was calculated as a non-inferiority clinical trial according to the literature (Blackwelder 1982). We expected that cervical dilation would be achieved in 96% of the cases using 400 µg of misoprostol and 86% in the 200 µg group. If there is a true difference in favour of the 400 µg treatment of 10% (96% vs 86%), then at least 184 patients were required in order to be 95% sure that the upper limit of a one-sided 97.5% confidence interval (or equivalently a 95% two-sided confidence interval) would exclude a difference in favour of the standard group of more than 25%.

The determination of non-inferiority margins was based on the literature (Hahn 2012; Wu et al. 2017; Kapp et al. 2010; Singh et al. 1998). It is known that 400 µg of misoprostol yields a 96% cervical dilation > 8 mm (Singh et al. 1998). We considered 86% of the 200 µg misoprostol group as the minimal acceptable percentage. The non-inferiority margin was determined by  $\frac{1}{3}$  of the difference between the 400 µg effect (96.7%), compared to the 200 µg dose (23.3%) found in the literature, i.e.  $73.4 / 3 = 24.46$ . (Fong, Singh, and Prasad 1998; Hahn 2012; Wu et al. 2017; Kapp et al. 2010; Singh et al. 1998).

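### The analysis section never applies the non-inferiority criterion: no planned step compares a confidence interval for the difference in proportions with the 25-point margin

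*Combined protocol and SAP*

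**What the plan says.** Several sections describe one design.

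- **Study design** calls the trial a two-arm parallel non-inferiority trial.
- **Study goals, Primary** asks whether priming with 200 µg is not "less than 25% at the dose of 400" µg.
- **Hypothesis** ("Our null hypothesis is that" …) puts this as a difference in proportions. The null is that the 400 µg proportion exceeds the 200 µg proportion by 25 points or more.
- **Variables** lists a binary outcome: "Cervical dilation present or not".
- **Sample size** gives the criterion. The upper limit of a one-sided 97.5% (two-sided 95%) confidence interval "would exclude a difference in favour of the standard group of more than 25" percent.

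**Statistical analysis**, the only analysis section, plans something else:

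- First, a Student's t-test, with a normality check or a transformation. The variable is not named but is apparently dilation in mm.
- If the test is not significant: "If there is no statistical difference between the groups, cervical dilation between each group can be verified with the Pearson (or Spearman) test", or a chi-square on <8 / ≥8 mm.
- If it is significant: correlations within each dose group.

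The section contains no difference in proportions, confidence interval, margin or non-inferiority decision.

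**The concern.** The design and the analysis answer different questions. The design asks whether 200 µg is worse by less than 25 points. The analysis asks whether the groups differ at all. A difference can be significant and still lie wholly inside 25 points, and a non-significant difference does not by itself rule out one above 25 points. The t-test result therefore does not settle the stated hypothesis, and the section does not say that it should. It names nothing else that does.

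Three consequences follow.

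- The 95% power belongs to a criterion that the analysis plan never applies.
- The first listed outcome, "Dilatation of the cervix without the need for a dilator between 3 and 6 hours after placing the misoprostol", has no analysis, although the case report form records whether dilation was adequate or Hegar dilators were used.
- Choices that should be fixed before data are seen stay open: the interval method, and which binary outcome is primary. Outcomes and the case report form point to no need for a dilator. Sample size supports its planning rate with the statement that 400 µg "of misoprostol yields a 96% cervical dilation > 8 mm".

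**Working it through.** **Inputs.** From Sample size: 96% (400 µg), 86% (200 µg), margin 25 points, two-sided 95% interval, 95% power, 184 patients. From Randomization: two arms in blocks of four. I assume 1:1 allocation, so 92 per arm.

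**Step 1: reproduce the plan's figure.** With unpooled variance,

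n per arm = [p₁(1−p₁) + p₂(1−p₂)] × (1.960 + 1.645)² / (0.25 − 0.10)²

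= (0.0384 + 0.1204) × 12.996 / 0.0225 = 91.7, so 92 per arm and 184 in total.

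This matches. The trial was sized for a margin-based comparison of proportions. Normal-approximation power at 92 per arm: SE = √(0.1588/92) = 0.04155, and Φ(0.15/0.04155 − 1.960) = 95.1%.

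**Step 2: how often the two questions diverge.** No SD in mm is given, so the t-test cannot be evaluated. An uncorrected chi-square at 5% stands in for it. The figures are exact binomial probabilities over all 93 × 93 outcomes at 92 per arm, with 96% for 400 µg. Rates other than 86% for 200 µg are assumptions.

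| 200 µg rate | Criterion met (Newcombe / Wald) | Difference significant | Both (Newcombe / Wald) |
|---|---|---|---|
| 86% | 91.1% / 93.2% | 68.9% | 60.0% / 62.0% |
| 88% | 97.2% / 98.1% | 53.0% | 50.1% / 51.0% |
| 91% | 99.8% / 99.9% | 26.8% | 26.5% / 26.6% |
| 96% | 100.0% / 100.0% | 4.3% | 4.3% / 4.3% |

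At the planning rates, the share of criterion-meeting trials that enter the significant branch is 0.600/0.911 = 66% (Newcombe) or 0.620/0.932 = 67% (Wald). With Yates' correction, significance falls to 56.5% and the share to 52% or 53%.

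**Step 3: one data set.** 88/92 vs 79/92 gives 95.7% − 85.9% = 9.8 points. The 95% CI is 1.3 to 18.7 (Newcombe) or 1.5 to 18.0 (Wald), inside 25 points either way. The chi-square p is 0.022 (0.042 with Yates). Non-inferiority is shown and the difference is significant, yet the plan would go on only to correlations within each dose group.

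**Step 4: the opposite error.** Could a trial fail the criterion and still be non-significant? With 96% for 400 µg and the four 200 µg rates above, the probability is below 1e-16. Reading 'no difference' as non-inferiority would be conservative there. This does not hold at lower rates (assumed, not in the documents): 9.9% (Newcombe) or 12.1% (Wald) at 70% vs 60%, and 16.0% or 21.2% at 60% vs 50%. The true difference in both cases is 10 points, so these are disagreements between two rules and not type I error rates.

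**The case against.** The strongest reply is that a decision rule already exists. Sample size gives the margin, the scale and the interval level, and Hypothesis gives the direction. On this reading, Statistical analysis covers only the mm outcome and the secondary goal ("To verify if there is a relationship between the dose of misoprostol and the degree of cervical dilation"), and any statistician would apply the interval criterion anyway. This limits the freedom to choose after the fact, and it stands to that extent. But the rule appears only as the rationale for N. Even on this reading the primary hypothesis has no planned analysis, and the interval method and primary outcome remain open.

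A second reply is that the two-thirds figure is not a property of this plan, because it uses a chi-square for a t-test and depends on the continuity correction. That is fair. About one half to two thirds is the honest range, and only as an illustration. That the two questions diverge does not depend on it.

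Third, if 8 mm dilation is the primary outcome, a chi-square on it is named. True, but it is optional, comes only after a non-significant t-test, and tests equality rather than the margin.

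Fourth, the correlations may be meant for the secondary goal and could be clarified instead of removed. For the non-significant branch this is reasonable. Within one dose group, however, dose does not vary, so a correlation there cannot describe a relation between dose and dilation.

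**Conclusion.** The concern holds and must be fixed. This is a mismatch between the hypothesis and the analysis, not only missing detail: the one analysis section, followed as written, never tests the primary hypothesis. At the protocol's planning rates with 92 per arm, about 52% to 67% of trials meeting the 25-point criterion would also show a significant difference and so receive no comparison of proportions. That range rests on 1:1 allocation, a chi-square in place of the t-test, and the choice of interval and continuity correction. The conclusion itself rests only on the text. At the planning rates the risk is a primary question left unanswered or answered by a method chosen later, rather than a false claim of non-inferiority.

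**What to change.** Replace the primary analysis in Statistical analysis with wording such as:

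> The primary analysis is the risk difference (400 minus 200 µg) in [the one primary binary outcome], in [named analysis set, with stated handling of missing outcomes], with a two-sided 95% confidence interval by [one named method]. Non-inferiority is concluded only if the upper limit is below the pre-stated margin, whatever any test for a difference shows.

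Then:

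- Name the primary outcome before data are seen, and make Outcomes, Sample size and the case report form agree on it.
- Use 25 points as the margin, as in the Primary goal, Hypothesis and Sample size calculation, or state explicitly that the derived 24.46 applies.
- Always run the mm and 8 mm comparisons, as secondary analyses where they are not the primary outcome.
- Delete the branching on significance. Delete the correlations, or define what is correlated with what.
- Restate the power for the chosen interval.

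**Cost.** Wording only, with N kept at 184. At 25 points, exact power is about 93% (Wald) or 91% (Newcombe) instead of the stated 95%. If 24.46 is chosen, power at 184 is 93.6% by normal approximation and about 92% (Wald) or 89% (Newcombe) exactly. Restoring 95% by the planning formula would take 0.1588 × 12.996 / 0.1446² = 98.7, so 99 per arm and 198 in total.

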## **METHODS**

### **Study design**

This will be a triple-blinded, non-inferiority, two-arm parallel randomized clinical trial (RCT) at Hospital de Clínicas de Porto Alegre (HCPA), following the parameters of CONSORT.

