## **Randomization**

Patients eligible for this study will be invited to participate in the research. After reading and signing the informed consent, patients will be submitted to a standardized interview and will be randomized to one of the two arms.

Patients will be randomly allocated to receive misoprostol 400 or 200  $\mu$ g. Randomization list was obtained from a web-based site ([www.randomization.com](http://www.randomization.com)) and divided into blocks of four. The randomization sequence will remain in sealed, opaque, sequential envelopes.

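### The planned Pearson/Spearman correlations do not serve the dose–dilation question: depending on the reading they are arbitrary, undefined or a repeat of a two-sample test

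*Combined protocol and SAP*

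**What the plan says.** The design is a "two-arm parallel randomized clinical trial (RCT"), and under Randomization "Patients will be randomly allocated to receive misoprostol 400 or 200" µg. The secondary goal is "To verify if there is a relationship between the dose of misoprostol and the degree of cervical dilation", with dilation split at 8 mm. The Outcomes section records dilation as the largest Karmann cannula that passes without resistance, described as a "continuous variable 4 to 11".

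The Statistical analysis section opens with "Statistical analysis to be used will be performed using Student's" t-test, with a transformation if the data are not normal. What follows depends on the result:

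- **No significant difference:** "cervical dilation between each group can be verified with the Pearson (or Spearman) test using the continuous variables of both groups (dilation"), or alternatively a chi-square test on dilation below 8 mm against 8 mm or more.
- **Significant difference:** "the correlations will be by groups, i.e., 400 µg and 200 µg".

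Dilation is the only variable named for the correlation. The section mentions no effect estimate or confidence interval for dilation in mm.

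**The concern.** A correlation needs two variables measured on the same unit. The plan names one variable and two groups of different women. The sentence cannot mean Pearson's chi-square, because it refers to continuous variables and offers chi-square separately.

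Two things are at stake. An analyst who follows the text could report a coefficient that carries no information about dose. And because the pooled correlation is run only after a non-significant t-test, a second non-significant result could be presented as independent support for the doses being alike. In a non-inferiority trial that would mislead, since one reading merely repeats the t-test and another is blind to any difference between the arms.

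**Working it through.** **Inputs.** From the documents: independent arms; doses 400 and 200 µg; expected rates 96% and 86%; margin 25 points; one-sided 97.5% confidence limit; 95% power; 184 patients. Assumed: 1:1 allocation (the Randomization section gives blocks of four but no ratio); that the t-test is applied to dilation in mm (the section does not name its variable); and, for simulation only, an SD of 1.5 mm and the means given below, because the documents give neither.

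**The plan's own figure.** n per arm = (1.960 + 1.645)² × (0.96×0.04 + 0.86×0.14) / (0.25 − 0.10)² = 12.995 × 0.1588 / 0.0225 = 91.7, so 92 per arm and 184 in total, as stated. This fixes the group size used below; nothing in this point disputes it.

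**Reading 1: dilation in one arm against dilation in the other.** No pairing exists, so the order of rows decides r. Over random pairings r has mean 0 and SD 1/√(92 − 1) = 0.105, so a 95% range of about ±1.96 × 0.105 = ±0.21. Shifting every value in one arm by a constant leaves r unchanged, so r cannot register a difference in means. Simulation (normal data, mean 9 mm in one arm, SD 1.5 mm, 92 per arm, 2000 re-pairings of one data set per row):

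| True shift | t-test p | 95% range of r | Share with p < 0.05 |
|---|---|---|---|
| 0 mm | 0.70 | -0.19 to 0.20 | 4.3% |
| 1 mm | 1×10⁻⁹ | -0.20 to 0.20 | 5.0% |
| 3 mm | 7×10⁻²³ | -0.21 to 0.21 | 5.3% |

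Only the first row would enter the plan's pooled branch. The other two show that r does not respond to dose at all.

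**Reading 2: dose against dilation within an arm.** r = cov(dose, dilation) / (SD of dose × SD of dilation). Within an arm dose is constant, so its SD is 0 and r is 0/0. The software returned an undefined value.

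**Reading 3: dose against dilation, arms pooled.** With a two-valued dose, t = r√[(N − 2)/(1 − r²)] with N − 2 = 182, which is the equal-variance t statistic itself. Over 1000 simulated trials the Pearson and t-test statistics and p-values agreed to within 10⁻¹⁴. The branch needs |t| < 1.973 (two-sided 5%, 182 df), which forces |r| < 1.973/√(1.973² + 182) = 0.145. On the same data, Pearson is therefore non-significant before it is computed. Pooled Spearman p-values matched the rank-sum p-values to within 0.0015. With dilation split at 8 mm, N×r² equalled the uncorrected chi-square statistic to rounding.

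**What the usable analyses would give.** Take underlying means of 10.6 and 9.6 mm with SD 1.5, rounded down to whole mm and limited to 4–11. The chance of at least 8 mm is Φ(2.6/1.5) = 96% and Φ(1.6/1.5) = 86%, matching the planning rates. The mean difference averaged about 0.84 mm with SE 0.19, an interval of about 0.84 ± 1.96×0.19 = 0.47 to 1.21 mm. At the planning rates the risk difference is 10 points with SE √(0.1588/92) = 4.2 points, or 10 ± 8.1 points.

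**The case against.** The strongest reply is that the plan still holds together without the correlation. Much of that stands.

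- A reader might infer that the secondary goal has no valid test. The documents do not support this: the chi-square test sits in the same sentence and uses the goal's own 8 mm cut.
- A reader might infer that no reading of the correlation measures a dose effect. That is too strong. Pooled Pearson does so redundantly, and pooled Spearman is close to a rank-sum test, which is a legitimate comparison and not a duplicate of the t-test.
- A reader might infer that the millimetre data are never properly compared. The t-test comes first and compares arm means. The missing estimate and interval are a reporting gap, not a result of the correlation wording.
- A reader might picture the pooled correlation masking an obvious dose effect. Under the 96%/86% scenario above, only between about 0.4% and 1% of simulated trials had a t-test p of 0.05 or more, so that branch would rarely be reached.
- The rule of pooling if the arms agree and splitting if they differ would suit a correlation of dilation with a covariate on the case form, such as gestational age or parity. That is computable, but no covariate is named and it would not answer a question about dose.

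The wording is also permissive and concerns a secondary analysis. None of this gives the correlations a use for the dose–dilation question that the two-sample tests do not already serve.

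**Conclusion.** The point holds for the correlation wording alone. The arbitrary, undefined and redundant results follow from the parallel design and the two fixed doses; they do not depend on the simulated means or SD. The Pearson identity applies to the equal-variance t-test on the same data, transformed or not. The illustrative sizes in mm do rest on the assumed means and SD.

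The consequence is moderate. The secondary goal keeps a valid test, and the primary comparison and sample size are untouched. The correction is worth making because this section is the whole analysis plan, and a correlation reported from it could be read as evidence on dose.

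**What to change.** In the Statistical analysis section, delete the Pearson/Spearman wording, the condition on a non-significant t-test, and the last sentence on correlations by group. Do not delete the sentence containing the chi-square test as a whole, since that would remove the named test for the secondary goal. Replacement text could read:

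> Dilation in mm will be compared between all randomised women in the two arms by the mean difference (400 minus 200 µg) with its 95% confidence interval from Student's t-test. The proportion with dilation of at least 8 mm will be compared by the chi-square test and reported as a risk difference (400 minus 200 µg) with its 95% confidence interval. Both will be reported whatever the result of either.

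A rank-sum test may be added as a sensitivity check. A Hodges–Lehmann shift is less suitable as the main estimate: on whole-mm data its 95% interval collapsed to zero width (1 to 1 mm) in about 30% of simulated trials, which the mean difference did not do.

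If a correlation with a recorded covariate is wanted, name the covariate, label the analysis exploratory, and state that it is not evidence on dose.

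The cost is a few lines of text, with the same data and no extra patients.

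### The between-dose comparison at 8 mm, which is the secondary objective, is optional and depends on another test; if that test shows a difference, only within-dose correlations are planned

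*Combined protocol and SAP*

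**What the plan says.** The Secondary part of the study goals reads "To verify if there is a relationship between the dose of misoprostol and the degree of cervical dilation", with dilation split at 8 mm or more versus less. The Outcomes section lists "Dilatation of the cervix with 8mm" as outcome 2 and describes a Karmann cannula measurement on a scale from 4 to 11.

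The Statistical analysis section is a single paragraph. It opens with a Student's t-test, after a transformation if the data are not normal, and does not name the variable tested. It then branches:

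- **No difference:** "If there is no statistical difference between the groups, cervical dilation between each group can be verified with the Pearson (or Spearman) test" on the continuous values, "or the chi-square test dilation <8, ≥8mm".
- **Difference:** "If there is a statistical difference between the groups, the correlations will be by groups", meaning 400 µg and 200 µg separately.

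The Sample size section expects that "cervical dilation would be achieved in 96% of the cases using 400 µg of misoprostol and 86% in the 200 µg group". It cites literature in which 400 µg "yields a 96% cervical dilation > 8 mm", and it sizes the trial on a two-sided 95% confidence interval for the difference.

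**The concern.** A stated objective should have an analysis that is carried out whatever the other results show. Here the only test named at the 8 mm cut sits in one branch, and even there it is an alternative to a correlation. The other branch names nothing that compares doses at 8 mm.

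Two things are at stake. The secondary objective can end without a between-dose result. And whether it gets one, and in what form, depends on another test and on a choice the analyst can make after seeing the data. If the first test is on dilation in millimetres, the comparison is lost when the doses appear to differ, which is when its size matters most.

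**Working it through.** **Step 1. Objective against planned analysis.**

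| Result of the first test | Analysis named | Compares doses at 8 mm? |
|---|---|---|
| No difference | Pearson or Spearman on continuous dilation, or chi-square at 8 mm | Only if the chi-square is the option chosen |
| Difference | Correlations within 400 µg and within 200 µg | No: dose is constant within each group |

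No other section gives an unconditional analysis of the 8 mm outcome.

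**Step 2. Possible readings of the first test.** The variable is unnamed.

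- *Dilation in mm.* The 8 mm comparison is absent when the doses differ. The t-test is then itself a dose comparison, but of means. It gives neither a difference in the proportion reaching 8 mm nor an interval for one.
- *A baseline variable.* The 8 mm comparison depends on a baseline test, and remains optional even in the favourable branch.

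It is conditional and optional on both readings.

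**Step 3. The plan's own sample size.** Inputs from the Sample size section: 96% versus 86%, margin 25 points, one-sided 0.025, power 95%. Equal allocation is assumed, since the ratio is not stated.

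n per arm = (1.960 + 1.645)² × (0.96 × 0.04 + 0.86 × 0.14) / (0.25 − 0.10)² = 12.99 × 0.1588 / 0.0225 = 91.7, rounded up to 92, so 184 in total. The stated figure is reproduced.

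**Step 4. An example of what could go unreported.** Assume that both planning rates are 8 mm rates. The counts nearest to 96% and 86% of 92 are 88 and 79.

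- Proportions: 88/92 = 95.65%; 79/92 = 85.87%; difference 9.78 points.
- Wilson 95% limits: 89.35% to 98.30% (400 µg); 77.31% to 91.55% (200 µg).
- Newcombe lower limit: 9.78 − √[(95.65 − 89.35)² + (91.55 − 85.87)²] = 1.3 points.
- Newcombe upper limit: 9.78 + √[(98.30 − 95.65)² + (85.87 − 77.31)²] = 18.7 points.
- Pearson chi-square: 184 × (88 × 13 − 79 × 4)² / (92 × 92 × 167 × 17) = 5.25, p = 0.022; with continuity correction p = 0.042. The smallest expected count is 92 × 17 / 184 = 8.5.

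**Step 5. Sensitivity to the assumed rates.** The Sample size section ties only the literature 96% to 8 mm, so a range is needed. The expected Newcombe 95% CI width for a 10-point difference with 92 per arm, by exact binomial enumeration, is:

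| True rates | Expected width (points) |
|---|---|
| 96% vs 86% | 17.1 |
| 90% vs 80% | 20.7 |
| 80% vs 70% | 24.6 |

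These widths show how precise the omitted result would be. They do not say how often it would be omitted, which depends on the unnamed variable and its distribution.

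**The case against.** The best counter-argument is that the text is silent rather than restrictive. The sentence for the difference branch governs correlations and does not withdraw the chi-square. The first test may also be a check that the arms are comparable; under randomisation the no-difference branch would then be the usual route, and that branch does name the chi-square. This weakens any claim that the comparison will usually be lost, and none is made here. It does not make the comparison unconditional, and the chi-square remains one option among alternatives.

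A second argument is that the hypothesis and sample size already commit the trial to a difference in proportions judged by a 95% interval, possibly at 8 mm. That is a fair point about intent. But those sections state a hypothesis and size the trial, and the Statistical analysis section does not carry the interval forward.

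A third is that the case report form has no explicit field for the largest cannula passed without resistance: it records Karmann cannula numbers beside adequate dilation and Hegar dilator numbers beside unsuitable dilation. This is worth checking, but the plan's own chi-square needs the same measurement, so it is not a cost of this change.

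Finally, the within-group correlations could be kept as harmless extras. They could, but they do not answer the objective and their second variable is not stated.

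**Conclusion.** The concern holds. As written, the secondary objective can be left without a between-dose analysis at 8 mm, and whether it receives one depends on another test and on the analyst's choice. That it is conditional and optional follows from the text on any reading. That it drops out when the doses differ rests on reading the first test as one on dilation in millimetres.

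No frequency of loss is given, because the documents do not supply what is needed to calculate one. The example of 9.8 points (95% CI 1.3 to 18.7) rests on 92 per arm and on treating both planning rates as 8 mm rates. The change should be made; the objective is secondary and its measurement is already in the procedure.

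**What to change.** Delete the branching and the within-group correlations from the Statistical analysis section. State instead that the difference between doses in the proportion with dilation of at least 8 mm will always be reported with its 95% confidence interval, in all randomised women, whatever any other test shows. State also that a cervix admitting no cannula counts as less than 8 mm; this follows from the 4 to 11 scale and keeps the poorest responders in the denominator.

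The cost is analysis wording only. The cannula measurement is already in the Outcomes procedure and the sample size stays at 184. When making the edit, confirm that the case report form captures the largest cannula passed for every woman.
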